4.3 Exclusion criteria

A potential subject who meets any of the following criteria will be excluded from participation in this study:

Cocogen Trial

- Patient refusal to comply to protocol procedures or schedule
- Local or systemic infection (bacteraemia)
- Evidence of inflammatory arthritis or an inflammatory systemic disease responsible for knee pain
- Intra-articular injections (steroids, hyaluronic acid, platelet enriched plasma, ...) in the index knee during the 3 months prior to procedure
- Body mass index (BMI) > 40 kg/m²
- Pregnant, nursing or planning to become pregnant before the treatment. Women of reproductive age will be tested on pregnancy prior to start of the study. Participants who get pregnant after the treatment during the follow up period will not be excluded.
- Chronic widespread pain
- Patients with psychosocial dysfunction will be referred for further psychological follow up prior to possible inclusion
- Allergies to products used during the procedure
- Uncontrolled coagulopathy defined as supratherapeutic dose of anticoagulation medication.
- Uncontrolled immune suppression
- Participating in another clinical trial/investigation within 30 days prior to signing informed consent
- Patient is currently implanted with a defibrillator, neuromodulator or other electrical devices
- Radicular pain in index leg
- Patient received previous conventional or cooled radiofrequency of the index knee

4.4 Sample size calculation

The primary aim of this study is to provide estimates of the effect sizes of the primary and secondary outcome measures, and to estimate the inclusion rate so that we have sufficient input to determine feasibility of a future RCT and to yield input for the sample size calculation. Further design aspects, such as the need for multilevel analysis based on clusters of patients within hospitals will be assessed as well. A rule-of-thumb suggests including 12 patients per group in case of a pilot study, so that preliminary data on effect sizes and feasibility can be obtained. (30) For our study, this means 12 patients in the conventional RF group and 12 in the cooled RF group, but separately for patients with osteoarthritis and for patients with knee pain after total knee arthroplasty. Hence, we will include a total of 48 patients.

Cocogen Trial

5. TREATMENT OF SUBJECTS

5.1 Investigational treatment

Procedure description

According to the recent ASRA and ESA guidelines on peripheral blockade in the anticoagulated patient, management should be based on site compressibility, vascularity, and consequences of bleeding, should it occur. (31) In the genicular radiofrequency treatment performed in this study, we judged this factors to be in favour of not stopping anticoagulation.

During the procedure the patient is monitored using pulse oximetry. No sedation is administered so the patient is able to communicate and report the stimulation adequate. The patient is placed in a supine position on a fluoroscopy table with the index knee flexed 10-15° by placing a cushion in the popliteal fossa. The procedure is performed under sterile conditions. The procedure is performed with a 100 mm long, 18 G straight RF cannula/introducer (Halyard) with a probe/electrode with a 10 mm active tip or with a 100 mm long, 17 G RF cannula/introducer with an 18 G cooled probe/electrode with a 4 mm active tip (Halyard/Coolief). No diagnostic block is performed since a recent study showed no prognostic value. (32) No corticosteroids are injected to decrease the risk of complications such as systemic effects and infection. (33) Using a high frequency linear ultrasound the superomedial, the superolateral and the inferomedial genicular nerve are targeted described as below. The inferolateral genicular nerve is not targeted because of its proximity to the common peroneal nerve with its motor branches.

Superomedial genicular nerve

The transducer is placed in a coronal orientation on the medial side of the proximal knee. After identifying the femoral medial epicondyle, the transducer is displaced proximally and centered to the junction between the epiphysis and diaphysis of the femur and the vastus medialis superficial to it, just anterior to the adductor tubercle. The superomedial genicular artery may or may not be seen between the deep fascia of the muscle and the femur at this level. If the superomedial genicular artery is visualised just above the bony cortex, the target point is next to this artery. If the artery is not visualised, the junction between the epiphysis and diaphysis is the target point. The probe-to-target point distance is assessed with ultrasound. An out-of-plane entry point is marked perpendicular to the center of the probe at the assessed probe-to-target point distance. Consecutively, the transducer was turned 90° into the transverse plane at this point. The skin and soft tissue are anesthetized with 1 ml lidocaine 2% at the estimated entry point. The cannula is advanced using an anterior to posterior 'in plane' approach in the transverse plane until contact is made with the bony

Cocogen Trial

cortex at the center of the femur. A RF electrode is introduced in the cannula. Sensory stimulation (50 Hz) is applied and produced paresthesia at a threshold of less than 0,5 V. The absence of fasciculations below 1 V is observed after motor stimulation at 2 Hz, confirming sufficient distance to relevant motor branches. If no sensory stimulation threshold is obtained at this position, the transducer is repositioned until sensory threshold is reached.

Inferomedial genicular nerve

The transducer is placed in a coronal orientation on the medial side of the distal knee to visualize the junction of the tibial medial epiphysis and diaphysis, the inferomedial genicular artery and the medial collateral ligament. If the inferomedial genicular artery is visualised just above the bony cortex beneath the medial collateral ligament at the midpoint between the tibial medial epicondyle and the tibial insertion of the medial collateral ligament, the target point is next to this artery. If the artery is not visualised, the junction between the epiphysis and diaphysis is the target point. The probe-to-target point distance is assessed with ultrasound. An out-of-plane entry point is marked perpendicular to the center of the probe at the assessed probe-to-target point distance. Consecutively, the transducer was turned 90° into the transverse plane at this point. The skin and soft tissue are anesthetized with 1 ml lidocaine 2% at the estimated entry point. The cannula is advanced using an anterior to posterior 'in plane' approach in the transverse plane until contact is made with the bony cortex at the center of the tibia. A RF electrode is introduced in the cannula. Sensory stimulation (50 Hz) is applied and produced paresthesia at a threshold of less than 0,5 V. The absence of fasciculations below 1 V is observed after motor stimulation at 2 Hz, confirming sufficient distance to relevant motor branches. If no sensory stimulation threshold is obtained at this position, the transducer is repositioned until sensory threshold is reached.

Superolateral genicular nerve

The transducer is placed in a coronal orientation on the lateral side of the proximal knee. After identifying the femoral lateral epicondyle, the transducer is displaced proximally to image the junction between the epiphysis and diaphysis of the femur and the vastus lateralis superficial to it. The superolateral genicular artery may or may not be seen between the deep fascia of the muscle and the femur at this level. If the superolateral genicular artery is visualised just above the bony cortex, the target point is next to this artery. If the artery is not visualised, the junction between the epiphysis and diaphysis is the target point. The probe-to-target point distance is assessed with ultrasound. An out-of-plane entry point is marked perpendicular to the center of the probe at the assessed probe-to-target point distance. Consecutively, the transducer was turned 90° into the transverse plane at this point. The skin and soft tissue are anesthetized with 1 ml lidocaine 2% at the estimated entry point. The

Cocogen Trial

cannula is advanced using an anterior to posterior 'in plane' approach in the transverse plane until contact is made with the bony cortex at the center of the femur. A RF electrode is introduced in the cannula. Sensory stimulation (50 Hz) is applied and produced paresthesia at a threshold of less than 0,5 V. The absence of fasciculations below 1 V is observed after motor stimulation at 2 Hz, confirming sufficient distance to relevant motor branches. If no sensory stimulation threshold is obtained at this position, If no sensory stimulation threshold is obtained at this position, the transducer is repositioned until sensory threshold is reached.

[figure not shown]

Fig. Ultrasound probe position and corresponding images for genicular radiofrequency treatment. Color Doppler shows the corresponding genicular arteries. Treatment sites are marked with yellow asterisks.

If all three target nerves were identified, a control fluoroscopy image is made to confirm the needle tip position. First, an AP view is made and the needle tip should be at the junction between the diaphysis and the epiphysis touching the bony cortex. Second, a lateral view is made where the needle tip should be within the 2 middle quarters of the femur width.

If the needle tip is confirmed to be in the correct position 1 ml of lidocaine 2% is injected before the start of a RF treatment. In the conventional radiofrequency group a treatment of 80°C at the tip is applied during 90 seconds at each nerve. In the cooled radiofrequency 18

Cocogen Trial

group a treatment of 60°C measured at the tip and on average 80°C in the targeted tissue is applied during 150 seconds using the Coolief system.

After the procedure, the patient is transferred to the recovery. After 30 minutes without any events, the patient is discharged at home. Home medication is continued postoperative. Patient is informed about potential transient increase in pain due to neuritis and alarm symptoms (fever, swelling, bleeding and motor weakness).

5.2 Use of co-intervention

It is allowed to use other medication or undergo an intervention as long as documented to be able to adequate estimate costs.

5.3 Escape medication

The use of all medication is allowed as long as documented. This enables the researchers to adequate estimate costs.

Cocogen Trial

6. NON-INVESTIGATIONAL PRODUCT

The medical products used in this study are used as in usual clinical practice. The 'CE certificates' and 'instructions for use' of each medical product are to be found in Appendix B and C.

6.1 Name and description of non-investigational product(s)

The following is a summary description of the used study device. For additional information, please refer to the COOLIEF "Instructions for Use" (Appendix B). The COOLIEF™ system is composed of three primary components (collectively known as 'disposables') and is used in conjunction with the pain management generator, pump unit, connector cables (collectively known as 'Hardware') and dispersive electrodes (also known as 'grounding pads'):

- Cooled radiofrequency sterile tube kit (sterile, single use, non-body contact): it is used for closed-loop circulation of sterile water through a Halyard cooled radiofrequency probe. It includes a burette and tubing.
- Cooled radiofrequency introducer (sterile, single use, 100 mm, 17 gauge, straight): it is to be used with the probes only. The cooled radiofrequency introducer provides a path for the probe to the targeted nervous tissue.
- Cooled radiofrequency probe (sterile, single use, 18 gauge): it is inserted through an introducer into or near nervous tissue. The active tip extends 4 mm from the introducer and delivers energy. Sterile water circulates internally to cool the probe while it delivers radiofrequency energy. A thermocouple in the probe measures the cooled electrode temperature throughout the procedure.

The product is comprised of an electrically insulated shaft with an active tip that functions as an electrode for RF energy delivery, a handle, tubes with luer locks and a cable with a 7-pin connector. The introducer includes an insulated stainless steel cannula and a stylet. The tube kit is comprised of a burette and flexible tubing fitted with luer locks for connection to the probe.

The following is a summary description of the used control device. For additional information, please refer to the "Instructions for Use" (Appendix C). The control device to produce a conventional radiofrequency lesion is composed of two primary components and is used in conjunction with the same pain management generator, connector cables and dispersive electrodes (also known as grounding pads) (Halyard) as in the study group.

Cocogen Trial

- Radiofrequency introducer (sterile, single use, 100 mm, 18 gauge, straight): it is to be used with the probes only. The radiofrequency introducer provides a path for the probe to the targeted nervous tissue.
- Radiofrequency probe (sterile, single use): it is inserted through an introducer into or near nervous tissue. The active tip extends 10 mm from the introducer and delivers energy. A thermocouple in the probe measures the electrode temperature throughout the procedure.

6.2 Summary of findings from clinical studies

The treatment performed with the COOLIEF[™] system is a well-established method for delivering lesions into nervous tissue to accomplish neurotomy procedures to deactivate nerves that are responsible for transmitting pain signals. (24). The system uses water-cooled technology to deactivate pain transmission. (24)

6.3 Preparation and labelling of Non Investigational Medicinal Product

The probe, introducer, and tube kit are ethylene oxide sterilized and supplied sterile. These components can be packaged together in a kit or as separate components. The devices should be stored in a cool, dry environment. The 'Instructions For Use' (IFU) documents (Appendix B and C) are included in each kit.

Cocogen Trial

7. METHODS

7.1 Study parameters/endpoints

Endpoints are chosen following the IMMPACT guidelines which recommend 6 core outcome domains in chronic pain research. (34) These domains are:

- 1. Pain
- 2. Physical functioning
- 3. Emotional functioning
- 4. Participant ratings of improvement and satisfaction with treatment
- 5. Symptoms and adverse events
- 6. Participant disposition

Furthermore, inclusion rate will also be monitored.

7.1.1 Main study parameter/endpoint

The primary study parameter is the proportion of patients with a pain reduction of at least 50% at three months post intervention. Pain intensity is expressed as a number from the numerical rating scale. Absolute NRS scores are also collected at each visit. A pain dairy of multiple NRS during 4 days will be collected to achieve a more complete and trustworthy idea of pain.

In this study we will use a threshold of 50% although IMMPACT guidelines only recommend a threshold of 30% because in the clinical setting the 50% threshold is most often used, as well in previous studies. This makes comparison within the literature easier.

NRS is a unidimensional, subjective measurement of pain intensity, expressed by the patient as a number between 0 and 10. It is a 11 point scale in which 0 equals no pain and 10 maximal pain. (35)

Furthermore, at one, three, six and twelve months post intervention the patients are also asked whether the pain is acceptable.

A month is defined as 30 days with 4 days before or after this timepoint.

At 12 months a time window of 2 weeks before and there the timepoint is accepted.

7.1.2 Secondary study parameters/endpoints

The secondary parameters are:

 Patient self-reported impression of change, measured by the Patient's Global Impression of Change (PGIC) at 1, 3, 6 and 12 months. The impression of change is measured using a 7 point likert scale. (36)

Cocogen Trial

- The change in medication use, measured by the change in Medication Quantification Scale III (MQS III). The MQS is designed as a methodology of quantifying different drug regimens in 1992 and updated in 1998 (MQS II) and 2003 (MQS III) using detriment weights determined by surveying physician members of the American Pain Society. (37) This will be recorded at baseline, 1, 3, 6 and 12 months post intervention.
- The duration of pain relief. This is defined as the time interval in which a NRS reduction of more than 50% is obtained or in which the pain is still acceptable without the usage of other additional therapies (increase in MQS 3 score of more than 50%, intra-articular infiltration, operation)
- The change in physical function from baseline to 3, 6 and 12 months post intervention. This will be measured by the change in the Oxford Knee Score (OKS). (38) The OKS is a patient-reported measure assessing pain intensity and physical function. The list consists of 12 items scored from 1 to 5, with 0 representing normal function/ least symptoms. Objectively, knee function will be measured through goniometry by using the CJOrtho app and by 'timed up and go' test. (39, 40) The measurement of maximal knee flexion and extension is performed in a standardised manner and photos of each position will be kept for review. The 'Timed Up and Go' test assesses patients' functional mobility of the lower extremities. Participants are timed with a stopwatch while standing up from a chair, walking 3 meters (in a comfortable and safe way), come back and sit back in the chair. The objective parameters of physical function will not be obtained at 12 months.
- The change in health-related quality of life, measured by the change in EQ-5D-5L, between baseline and 6 and 12 months post intervention. (41) The EQ-5D-5L is a patient-reported generic measure of HRQoL comprising five dimensions: mobility, self-care, usual activities, pain/discomfort and anxiety/depression. Responses to the 5 items (one for each dimension) result in a patient's health state that can be transformed into a utility score ranging between 0 (death) and 1 (full health), representing the quality of life of the health state. (41). The EQ-5D-5L is assessed at baseline and at 1, 3, 6 and 12 months post intervention.
- Change in characteristic attitudes and symptoms of depression from baseline to 3, 6 and 12 months post intervention. This will be measured by the change in Hospital Anxiety and Depression Scale (HADS) and in Pain Catastrophizing Scale (PCS) from baseline to 6 and 12 months. (42, 43) HADS is developed to detect anxiety and depression in patients with physical health problems. The questionnaire consists of 14 items: 7 items to measure anxiety and 7 items to measure depression. The PCS is often used in clinical settings to measure catastrophic thinking related to pain. The 13 item questionnaire consists of 3 subscales (magnification, rumination and helplessness) and asks patients to

Cocogen Trial

reflect on past painful experiences and to indicate the degree on which they experiences each of 13 thoughts of feelings on a 5- point scale (0 not at all and 4 all the time).

- Amount of Adverse Events and/or Serious Adverse Events. Active capture during each site visit to assess specific symptoms and adverse events that are relevant to chronic knee pain or RF treatment.
- Costs in both intervention groups. Costs include health care related costs (e.g. intervention cost, medication), costs to patients and family (e.g. travel costs, out-of-pocket payments), and costs due to lost productivity. Complete individual level hospital resource use data (e.g. surgical intervention, diagnostic procedures, hospital admissions, outpatient clinic visits) will be measured using medical records and by means of a self-developed questionnaire to be completed by patients, based on the iMTA Medical Consumption Questionnaire as recommended in the Dutch guideline for economic evaluation. (44) The questionnaire will have a recall period of 3 months and will be administered repeatedly at baseline, 3, 6 and 12 months post intervention. The Dutch manual for costing research will be used to determine prices for each volume of resource use. (45)
- Cost-effectiveness will be expressed using incremental cost-effectiveness ratios (e.g. incremental cost per QALY, incremental cost per reduced point on the pain score, and incremental costs per additional treatment success). QALYs (Quality Adjusted Life Years) will be calculated by multiplying life years with the health-related quality of life during these life years as measured by the EQ-5D-5L.
- At 12 months in the osteoarthritis group, we ask if a total knee arthroplasty is performed and if so at which timepoint.
- All used questionnaires to retrieve the above mentioned outcome parameters can be found in Appendix D.

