4.2 Inclusion criteria

In order to be eligible to participate in this study, a subject must meet all of the following criteria:

- Age ≥ 18 years
- Able to understand the informed consent form and provide written informed consent and able to complete outcome measures.
- Chronic anterior knee pain (> 12 months) with an NRS > 4 on most or all days for the index knee either constantly or with motion.
- Unresponsive to conventional treatments continued during 12 months including physiotherapy, oral analgesics or intra-articular infiltrations.
- Radiologic confirmation of arthritis of OA grade of 2 (mild), 3 (moderate) or 4 (severe) noted within 6 months for the index knee according the Kellgren Lawrence criteria (27) diagnosed by an independent radiologist with experience in musculoskeletal imaging on Rx or MRI (28) or patients with total knee arthroplasty of the index knee with a negative orthopaedic workout.
- Other therapies (including surgical interventions) for pain in the index knee are allowed for the period of the study follow up as long as they are documented. This is necessary to correctly estimate the costs in the cost effectiveness analyses. Allowing patients to receive additional treatments will also improve the protocol compliance.
- Agree to provide informed consent and to comply with the requirements of this protocol for the full duration of the study

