Appendix E

Table 1: Overview study procedures per site visit

Site visit	Study procedures at site	Study procedures at home
T0: baseline	- MQS III	- NRS
	- Goniometry	- Is pain acceptable?
	- Timed up and go test	- Medication list
		- OKS
		- EQ-5D-5L
		- HADS
		- PCS
		- Cost diary
T1: 1 months	- Adverse Events	- NRS
post	- MQS III	- Is pain acceptable?
intervention		- PGIC
		- Medication list
		- EQ5-5D-5L
		- Cost diary
T2: 3 months	- Adverse Events	- NRS
post	- MQS III	- Is pain acceptable?
intervention	- Goniometry	- PGIC
	- Timed up and go test	- Medication list
		- OKS
		- EQ-5D-5L
		- Cost diary
		- HADS
		- PCS
T3: 6 months	- Adverse Events	- NRS
post	- MQS III	- Is pain acceptable?
intervention	- Goniometry	- PGIC
	- Timed up and go test	- Medication list
		- Cost diary
		- OKS
		- EQ-5D-5L
		- HADS
		- PCS
T4: 12 months	/	- NRS

Cocogen Trial

- Is pain acceptable?
- PGIC
- Medication list
- Cost diary
- OKS
- EQ-5D-5L
- HADS
- PCS
- Adverse Events
- Performance of TKA?

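### Duration of pain relief (Section 7.1.2) can credit relief to a patient whose pain was already acceptable at baseline and did not improve, and its additional-therapy rule is incompletely specified

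*Protocol*

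**What the plan says.** Section 7.1.2 gives duration of pain relief two routes. The first is the NRS: "This is defined as the time interval in which a NRS reduction of more than 50% is obtained". The second is "or in which the pain is still acceptable without the usage of other additional therapies". A bracket then lists the additional therapies: "increase in MQS 3 score of more than 50%, intra-articular infiltration, operation".

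Other places bear on how this works:

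- Section 7.1.1 says that "at one, three, six and twelve months post intervention the patients are also asked whether the pain is acceptable". The table in Appendix E also lists "Is pain acceptable" at T0.
- The pain criterion in Section 4.2 is "Chronic anterior knee pain (> 12 months) with an NRS > 4 on most or all days for the index knee". It does not require that the patient find the pain unacceptable.
- The prior-treatment criterion in Section 4.2 is "Unresponsive to conventional treatments continued during 12 months including physiotherapy, oral analgesics or intra-articular infiltrations". It does not require current analgesic use.
- Section 4.2 also states: "Other therapies (including surgical interventions) for pain in the index knee are allowed for the period of the study follow up", provided they are documented. Section 5.2 repeats the allowance for any intervention. The RF exclusion in Section 4.3 covers only RF received before entry.
- The primary endpoint in Section 7.1.1 uses a reduction of at least 50%.
- Section 9.2 reports duration as a difference between arms with a 95% confidence interval, as exploratory.

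**The concern.** Acceptability is a state, and relief is a change. Joining the two routes with a plain alternative makes the state sufficient by itself. An endpoint named for relief can then be met with no change at all, by a patient whose baseline answer already showed that the pain was acceptable.

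The condition that ends the interval has gaps of its own. Two analysts working from this text could reach different durations for a patient who had an infiltration, a second RF treatment, or a first analgesic after starting with none.

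This matters because Section 7.2 names longer success as a potential benefit of cooled RF. Section 4.4 says the pilot should supply effect sizes for secondary as well as primary outcomes, and Section 1 says that the pilot mirrors the future trial closely. An unclear definition would probably be carried forward.

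**Working it through.** **Sample size, for scale.** Section 4.4: 12 per group × 2 arms × 2 populations = 48. This reproduces the stated total.

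**1. The acceptability route.** Read literally, relief = (NRS reduction > 50%) or (acceptable and no listed therapy). Take whole-number baseline NRS from 5 to 10, which satisfies NRS > 4, and any follow-up NRS equal to or worse than baseline. The number of pairs is 6 + 5 + 4 + 3 + 2 + 1 = 21. All 21 count as relief if the patient calls the pain acceptable and has no listed therapy. In 6 of them the NRS is unchanged, and in 21 − 6 = 15 it is worse.

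**2. The therapy condition.**

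- *Scope.* The condition stands after the second route. If it governs only that route, a patient whose NRS falls by more than 50% after an infiltration remains in relief. If it governs both, the interval ends. The text does not settle which.
- *List.* It has three items and no wording that marks them as examples. Repeat RF or another nerve procedure on the index knee is not among them, yet Sections 4.2 and 5.2 permit any documented intervention. On the text, relief regained through repeat RF continues the count.
- *Baseline MQS of 0.* The percentage rise is (MQS at visit − MQS at baseline) / MQS at baseline. With 0 in the denominator it is undefined. Rewritten as MQS at visit > 1.5 × MQS at baseline, it becomes MQS at visit > 0, so any new analgesic meets it. Section 4.2 makes a baseline of 0 possible. The protocol does not say how common it will be.

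**3. The cut-off.** For whole-number baselines from 5 to 10, a reduction of exactly 50% occurs at 6 to 3, 8 to 4 and 10 to 5. Each is a success on the primary endpoint and fails the NRS route for duration.

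**4. Effect on the comparison.** Let x be the share in each arm held in relief to 12 months by acceptability alone. The protocol gives no x; 10%, 20% and 30% are assumptions.

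- *Case A: these patients have no treatment effect in either arm.* Their true duration is 0 and the recorded duration is 12 months. Each arm mean rises by 12x: 1.2, 2.4 or 3.6 months. The difference changes by 12x − 12x = 0.
- *Case B: these patients would otherwise have shown the average arm difference d.* The observed difference is (1 − x)d. For an illustrative d of 3 months: 3 × 0.9 = 2.7, 3 × 0.8 = 2.4, 3 × 0.7 = 2.1 months.

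The effect on the difference therefore depends on who these patients are. In so small a study chance also counts: one patient recorded at 12 months instead of 0 moves the mean of a 12-patient group by 12/12 = 1 month.

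**The case against.** The best defence is that the word still, under an endpoint named pain relief, implies that an achieved state continues. Entrants have had more than 12 months of pain, did not respond to treatment and accept an invasive procedure, so few may call their pain acceptable at T0. This is plausible, and it is a reason not to assume a large x. But no such condition is written, and asking the question at T0 allows for a yes.

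It can also be said that the therapy phrase may be read as covering both routes, that handling a zero denominator commonly belongs in an SAP, and that documented co-interventions can be dealt with in analysis. Each is fair and lowers the weight of those items. However, the protocol itself fixes the list and the percentage, so an SAP would have to amend them, not just fill them in.

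Acceptable pain is a legitimate patient-judged outcome, and a percentage rise in MQS is a legitimate choice. Neither is an error.

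Three stronger readings are tempting, and the documents do not support them:

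- *That the definition pulls the arms together and so favours conventional RF.* Equal time added to both arms by patients without any effect leaves a mean difference unchanged (case A). Shrinkage needs the further assumption of case B.
- *That the arm difference shrinks by 10% to 30%.* Those shares are assumed, and nothing in the protocol supports them.
- *That durability rests on this endpoint alone.* NRS at 6 and 12 months, PGIC and OKS also inform it.

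**Conclusion.** The point holds as a defect of definition. As written, Section 7.1.2 can record relief in a patient who did not improve. It also leaves open which events end the interval, and it treats a reduction of exactly 50% differently from the primary endpoint.

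The consequence is inflated mean durations in both arms. The between-arm difference is diluted only to the extent that patients with acceptable pain at baseline would otherwise have differed between arms. The size cannot be given from the documents. The T0 answers will show how many patients are at risk.

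Severity is minor to moderate. The endpoint is secondary and exploratory in a pilot of 48, and the rule in Section 9.2 for moving to the larger trial uses the proportion with treatment success, not duration. It deserves correction because the pilot is meant to yield effect sizes for secondary outcomes and because longer duration is a benefit attributed to cooled RF.

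**What to change.** Amend Section 7.1.2 for the endpoint definition only, with no change to which treatments patients may receive:

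1. Let the acceptability route count only for patients who answered not acceptable at T0, and assess the others on NRS alone. Alternatively, report NRS-based duration and acceptability as two separate outcomes. Mention the T0 question in Section 7.1.1 so that it matches Appendix E.
2. State that the additional-therapy condition applies to both routes.
3. Reconcile the therapy list with Sections 4.2 and 5.2, so that repeat RF or another nerve procedure on the index knee ends the counted interval.
4. State that any increase meets the MQS rule when baseline MQS is 0. The 50% rule can stay for other patients.
5. Change the NRS cut-off to at least 50%, to agree with Section 7.1.1.

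The cost is wording. Acceptability at T0, MQS or the medication list, and co-interventions are already collected. Items 1 to 3 will make reported durations somewhat shorter and less comparable with reports that use acceptability; item 5 works slightly the other way for patients at exactly 50%.
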